**A randomized placebo-controlled single center pilot study of the safety and
efficacy of tralokinumab in subjects with moderate to severe alopecia areata**

PI: [name]

NCT02684097

Document date: 8-11-2015

A randomized placebo-controlled single center pilot study of the safety and efficacy of tralokinumab in subjects with moderate to severe alopecia areata

PI: [name]

NCT02684097

Document date: 8-11-2015

A randomized placebo-controlled single center pilot study of the safety and efficacy of tralokinumab in subjects with moderate to severe alopecia areata

Institution:

Icahn School of Medicine at Mount Sinai
Department of Dermatology

[REDACTED], [name]
[name]
[contact]
[contact]

Investigators:

Principal Investigator:
[name], PhD

Co-investigators:
[name]

Protocol Version: April 21, 2015

Amendment # 1: August 11, 2015

Amendment #2: September 30, 2015

HYPOTHESES:

Primary Hypothesis:

1. It is hypothesized that IL-13 is involved in the pathogenesis of alopecia areata (AA).

Secondary Hypothesis:

1. Tralokinumab is superior to placebo for induction of hair regrowth in patients with moderate to severe alopecia areata, and will result in improved clinical outcomes for subjects with concomitant atopic dermatitis (AD).

OBJECTIVES and ENDPOINTS:

Primary objective

- 1) This is a pilot study intended to look at IL-13 associated cellular and molecular markers in the skin of patients with alopecia areata and to gain some insight into whether blocking IL-13 with Tralokinumab will affect those markers and hair regrowth

Secondary objectives

- 1) To study the safety of tralokinumab in patients with moderate to severe alopecia areata.
- 2) Study the safety of tralokinumab in patients with concomitant moderate to severe alopecia areata and atopic dermatitis.
- 3) Study the mechanism of action of tralokinumab in patients with moderate to severe alopecia areata.
- 4) Study the mechanism of action of tralokinumab in patients with concomitant moderate to severe alopecia areata and atopic dermatitis.

Primary endpoints

- 1) Change from baseline in cellular, and molecular markers in skin biopsies after treatment.

Secondary endpoints

- 1) Percentage change from Baseline in the Severity of Alopecia Tool (SALT) at Week 24.
- 2) Percentage of patients achieving 50% or greater improvement in their SALT score (SALT₅₀) at Week 24, compared to Baseline.

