If a subject is being discontinued prior to Week 24, the following procedures should be performed for the Early Termination visit: limited physical examination, pregnancy test (if applicable), assessment of regrowth pattern, SALT scoring, AASIS, AA-QoL, SCORAD, EASI and IGA scores (in subjects with AD only), clinical photography, assessment of concomitant medications, assessment of adverse events, and blood tests for chemistry and hematology, mechanistic studies, RNA, proteomic analysis, anti-drug antibody (ADA) measurement, and serum tralokinumab levels. In addition, biopsies of the scalp (one biopsy close to the area that was biopsied at Baseline) and skin (in subjects with AD only, one biopsy close to the area that was biopsied at Baseline) will be performed.

If a subject is being discontinued prior to Week 40 (but has completed Week 24), the following procedures should be performed for the Early Termination visit: limited physical examination, ECG (if not completed at Week 32), assessment of regrowth pattern, SALT scoring, AASIS, AA-QoL, SCORAD, EASI and IGA scores (in subjects with AD only), clinical photography, assessment of concomitant medications, assessment of adverse events, and blood tests for chemistry and hematology.

Subjects will not receive any other active treatment for alopecia areata or atopic dermatitis (outside of the study drug) while participating in the study.

Safety, laboratory, and clinical assessments will be performed at specified clinic visits. A

serum pregnancy test will be performed at Screening and urine pregnancy tests will be performed at Baseline and every 2 weeks prior to administration of the IP dose, if applicable.

Biopsies from the scalp will be performed on all subjects at Baseline and Week 24 or Early Termination visit. At Baseline, biopsies will be obtained from involved and uninvolved areas of the scalp. At Week 24 or Early Termination visit, the biopsy will be performed in the vicinity of the involved area biopsied at Baseline. An optional biopsy will be performed at Week 12, close to the area that was involved and biopsied at Baseline.

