Prior to beginning this study, approval for all study related documents (protocol, consent form, advertising) would be obtained from the Icahn School of Medicine at Mount Sinai Program for the Protection of Human Subjects (Institutional Review Board), [name].

DATA ANALYSES:

This is an exploratory study therefore sample size has been kept relatively low. Data collected from this study will be used to obtain estimates of differences and variability, of the change in treatment for IL-13. If the variability of the Post vs Pre differences are of the magnitude of the LS vs NL differences observed in preliminary data (SE=0.46) then the size of the confidence interval in differences could be observed in this study would be 0.58. As for the secondary outcome, the spontaneous regrowth rate in alopecia areata is 4%. To demonstrate efficacy of the study drug, a response rate of at least 50% is required. To be statistically significant, we would require a minimum of 10 subjects in the study, with an expected response rate of 0 or 1 subject in the placebo group.

MECHANISTIC STUDIES DATA ANALYSES:

For the comparisons of expression levels of lesional, and non-lesional AA skin, we will use RT-PCR, and gene-arrays. RT-PCR values will be normalized to the housekeeping gene hARP (validated in all our AD studies) and log2-transformed prior to analysis. Microarray data will be preprocessed using standard pipeline (exhaustively used by our group in a large number of studies) and log-2 transformed expressions. Adjustments by batch effect and clinical variables will be carried out if needed using ComBat. Mixed effect model on R's *limma* framework will be used and p-values for the moderated t-tests and paired-t-test will be adjusted by Benjamini-Hochberg procedure.

Extensive bioinformatics tools will be employed to gain insights on the results and test hypotheses that are generated in the "data mining stage". This will include (but is not be limited to) pathway and gene-set enrichment analyses using Ingenuity software, GSEA, the R package GSVA (Gene Set Variation Analysis) and other in-house codes produced by our group.

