To define cellular and molecular biomarkers of AA in skin biopsies, biomarkers will be divided into those that show significant group differences and those that do not. Multiple regression models will be used to determine the best set of biomarkers that predict disease activity and response. Similar approaches will be carried out for blood analyses.

Gene expression changes in Th2/IL-13, "T22"/IL-22, S100A7 and S100A8, Th1/IFN-gamma, and Th17/IL-17A will be jointly correlated with clinical responses by multivariate analysis using multivariate u-statistics and R package muStat, as we have previously reported.

DATA AND SAFETY MONITORING PLAN

Since this is a phase II study, with few subjects and minimal risks, this project will be monitored by the principal investigator, sub-investigators, and independent DSMB. Both the principal investigator will provide safety data to an independent Data and Safety Monitoring Board every 12 months. This DSMB will be comprised of dermatologists who are not directly related to this study. The DSMB will review all the safety data and provide a report of their findings to the Principal Investigator.

All non-serious events will be reported to the IRB and FDA (on behalf of the IND) on a yearly basis. All serious events will be reported to the IRB and FDA within 24 hours of becoming aware of the event.

Schedule of Events

Formatted: Left: 0.75", Right: 0.75", Top: 1", Bottom: 1", Width: 11", Height: 8.5"

Procedures	Screening (Day -28 to Day -1)	Base-line Day 0	Weeks 2, 6	Week 4	Week 8	Week 10	Week 12	Weeks 14 and 18	Weeks 16 and 20	Week 22	Week 24	Week 32	Week 40	Early Term Visit
Informed consent	X													
Inclusion/exclusion criteria	X	X												
Past Medical History (including demographic data and age on onset)	X													
ECG	X											X		X ⁶
Limited Physical Examination	X						X				X	X	X	X
Vital Signs ¹	X	X	X	X	X	X	X	X	X	X	X			
Chemistry and hematology	X	X		X			X				X	X		X ⁶
PPD or Quantiferon Gold	X													
HIV screening	X													
HBsAg, Anti-HBc antibody	X													
Pregnancy test ²	X	X	X	X	X	X	X	X	X	X				X ⁷
Assessment of Regrowth Pattern	X	X	X	X	X	X	X		X		X	X	X	X
SALT assessment	X	X	X	X	X	X	X		X		X	X	X	X
Subject Questionnaires AASIS and AA-QoL		X		X	X		X		X		X	X	X	X

Procedures	Screen-ing (Day -28 to Day -1)	Base-line Day 0	Weeks 2, 6	Week 4	Week 8	Week 10	Week 12	Weeks 14 and 18	Weeks 16 and 20	Week 22	Week 24	Week 32	Week 40	Early Term Visit
SCORAD, EASI, IGA ³		X		X	X		X		X		X	X	X	X

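### Data-mined pathways are to be tested with no independent data named, and Baseline lesional signatures tested pre/post within an arm can seem to normalise without a drug effect

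*Combined protocol and SAP*

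**What the plan says.** All references are to the combined protocol and SAP.

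- **Mechanistic Studies Data Analyses, mining step.** "Extensive bioinformatics tools will be employed to gain insights on the results and test hypotheses that are generated in the" data-mining stage. The tools include "pathway and gene-set enrichment analyses using Ingenuity software, GSEA", GSVA and in-house code, and the list is expressly open.
- **Same section, multiplicity.** "p-values for the moderated t-tests and paired-t-test will be adjusted by Benjamini-Hochberg procedure". Nothing is stated for pathways or hypotheses picked after looking at the data.
- **Same section, contrast.** "For the comparisons of expression levels of lesional, and non-lesional AA skin, we will use RT-PCR, and gene-arrays". No tralokinumab-versus-placebo contrast of expression change is named here.
- **Same section, selection step.** For defining AA biomarkers in skin, "biomarkers will be divided into those that show significant group differences and those that do not".
- **Objectives and Endpoints.** The primary endpoint is "Change from baseline in cellular, and molecular markers in skin biopsies after treatment".
- **Study Design, biopsies.** "At Baseline, biopsies will be obtained from involved and uninvolved areas of the scalp". Later, "At Week 24 or Early Termination visit, the biopsy will be performed in the vicinity of the involved area biopsied at Baseline".

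The Data Analyses section calls the study exploratory and bases its one precision figure for IL-13 on Post versus Pre differences.

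**The concern.** Two separate problems arise.

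1. **Selection and testing on the same data.** A hypothesis suggested by a data set and then tested on that data set has already been favoured by chance. Its p-value does not have the stated error rate unless the calculation accounts for the whole search. Adjusting the moderated and paired t-tests does not do this for pathways selected by eye, by enrichment software or by in-house code.

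2. **A shared biopsy.** The lesional versus non-lesional contrast uses the Baseline lesional sample, and so does the change from Baseline to Week 24. A gene that ranks as up-regulated partly because its Baseline lesional value was high by chance will tend to fall at Week 24 whatever the treatment. Tested within the active arm, this fall looks like normalisation.

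The molecular change is the primary endpoint and the trial's main product. Chance pathways, or a partly artificial reversal of the disease signature, could be reported as effects of tralokinumab.

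**Working it through.** **The plan's own figure.** The point does not rest on a stated number, but 0.58 is the only precision figure for the molecular endpoint. The plan gives SE = 0.46 for lesional versus non-lesional, and the Figure 1 legend gives 6 patients. Assume that 0.46 is the SE of a mean: SD = 0.46 × √6 = 1.127. The 95% half-width for a within-arm change is then 2.120 × 1.127/√17 = 0.579 with 17 patients and 2.110 × 1.127/√18 = 0.560 with 18. The plan gives no n, confidence level or half/full width, so 0.58 is not uniquely reproducible. The reading nearest to the plan is a pre/post interval within the active arm: 27 expected completers at 2:1 give 18 active and 9 placebo.

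**Selecting among mined pathways.** With m independent null pathways tested at 5%, P(at least one p<0.05) = 1 − 0.95^m. The plan gives no m, so a range is shown.

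| m | P(at least one) |
|---|---|
| 5 | 23% |
| 10 | 40% |
| 20 | 64% |
| 50 | 92% |

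**The shared Baseline sample.** Let L0, N0 and L24 be the Baseline lesional, Baseline non-lesional and Week 24 values, independent with variance σ² and no treatment effect.

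- Cov(L0 − N0, L24 − L0) = −σ².
- Each difference has variance 2σ², so the correlation is −σ²/2σ² = −0.5.
- For a gene with true gap δ and observed gap D, the expected change is −½(D − δ), so the share of the gap that seems to close is ½(1 − δ/D).

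This is one half for a purely null gene (δ = 0) and approaches zero when δ is large relative to the noise. The −0.5 is a correlation, not an amount of normalisation. It also weakens if a lesion-specific component persists to Week 24. If that component has variance 2σ², Var(L0 − N0) = 4σ², the correlation is −1/√8 = −0.35, and the null-gene share falls to one quarter.

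**Simulation with no treatment effect.** Assumptions: 18 active and 9 placebo completers; per-biopsy SD 1.127/√2 = 0.797 for every gene; 10% of genes truly up; two-sided 5%; ordinary t-tests in place of limma. Up-regulated genes were selected on Baseline lesional versus non-lesional, either at p<0.05 or after Benjamini-Hochberg. Their mean change was then tested in the same patients.

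| True gap (log2) | Share of gap seeming to close | False within-active 'signature down' call (nominal 2.5%) |
|---|---|---|
| 0.5 | 19-22% | 64-99% |
| 1.0 | 2-5% | 15-71% |
| 2.0 | 0.3-2.5% | 5-68% |

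The low ends come from Benjamini-Hochberg selection and the high ends from p<0.05 selection with independent genes. Genes here were independent or correlated at 0.3 within blocks. The false-call rate depends heavily on this choice: a separate run with modest inter-gene correlation gave about 30% at a gap of 0.5 and 2-7% at 1.0-2.0. Correlation shared across all genes, rather than within blocks, lowers the rate because the signature mean is then less precise.

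**After the change.**

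- Comparing change between arms gave 3.0-6.7% in the first set of runs and at most about 6.5% in the second (nominal 5%), even with the signature taken from the same data.
- A signature from an independent cohort gave 0.3-4.0% within the active arm (nominal 2.5%), with apparent normalisation about zero.
- Neither the between-arm contrast nor the shared-sample argument deals with picking the best of many pathways by its own p-value. That needs advance definition, separate data, or adjustment over all candidates.

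**The case against.** The strongest reply has four parts.

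- **The study is declared exploratory.** It is a pilot and promises no confirmation. This stands, and it is why labelling mined results is enough and mining need not stop. It does not give the p-values their nominal meaning: the plan speaks of testing and does not call these results descriptive.
- **The plan does not say that the same patients are used, or that Benjamini-Hochberg is confined to genes.** Both are true. Use of the same data is an inference, though no other source is named. On multiplicity for pathways the text is silent rather than contrary.
- **A reader might infer that disease genes will seem to normalise.** The documents do not support that. It needs selection on Baseline lesional versus non-lesional, a test of Week 24 against Baseline in the same patients, and a test within an arm. The plan leaves this route open through the shared biopsy, the paired t-tests and the Post versus Pre planning, but does not prescribe it. The effect is also small for strongly up-regulated genes.
- **Randomised placebo cancels the bias.** It does in a between-arm comparison, and the simulation agrees. The mechanistic section simply does not state that comparison for expression change.

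It is also fair that IL-13, IFN-gamma and IL-17A were examined in a separate preliminary sample and are named in advance. This selection bias does not reach them.

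**Conclusion.** The point holds in two parts.

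First, p-values for mined pathways do not carry their nominal meaning as the plan stands. The size depends on how many pathways are searched: 40% to 92% chance of at least one false finding for 10 to 50, assuming independent null pathways and unadjusted 5% tests.

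Second, the regression-to-the-mean bias is real but conditional on a within-arm test of a signature derived from this trial's Baseline biopsies. It is substantial for weak or false-positive genes and small for strong ones. The simulated rates rest on an SD of 1.127 for all genes, 10% of genes up, gaps of 0.5-2.0 log2 and assumed inter-gene correlation. Of these, only the SE of 0.46 and the 6 preliminary patients come from the documents, and the wide spread should be read accordingly.

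It would go too far to conclude that the mechanistic results as a whole are invalid. The gene-wise tests under Benjamini-Hochberg and the markers named in advance are outside the mined-hypothesis problem. This is a cheap improvement to the plan that changes what can be concluded from mined results.

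**What to change.** Amend the mechanistic analysis section before unblinding:

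1. Test any signature or pathway selected on the trial's Baseline lesional versus non-lesional data as the tralokinumab-minus-placebo difference in change, not as Post versus Pre within an arm.
2. Define gene lists for the Th1, Th2/IL-13, Th17 and Th22 pathways and apply Benjamini-Hochberg across these sets. The lists must be written: Study Design names serum markers, and the mechanistic section names individual markers for correlation with clinical response. Neither defines gene sets.
3. Label all other mined results hypothesis-generating and describe any p-values attached to them as descriptive.

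The change is to SAP wording plus the work of fixing the lists; no visit or sample is added. There are two costs. The between-arm contrast is less precise: with SD 1.127, its 95% half-width is 2.060 × 1.127 × √(1/18 + 1/9) = 0.95, against 0.56 for the change within 18 active patients. And fewer mined results can be presented as tested.

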Fig 1. Figure 1 shows comparable cytokine expression of the defining Th2 cytokine/IL-13, the defining Th1 cytokine/IFN gamma, and the Th17/IL-23 cytokines/IL-17A and IL12/23p40 in AA and AD. Lesional psoriasis skin tissues show a significantly higher expression of both IL-17A and IFN gamma, with significantly lower expression of IL-13 as compared with both AA and AD. Significant decreases in mRNA expression of IL-13, and IL12/23p40 are seen after treatment with intralesional corticosteroids, without significant changes in the other cytokines. P value= 0.0002 for the IL-13, and p=0.1 for the IFN gamma lesional vs non-lesional alopecia skin comparisons. JAK3 shows similar activation in AA, AD, and Psoriasis. NL- non lesional skin from scalp of AA patients; L- lesional skin from scalp of AA patients; PTX- post intralesional steroid treatment skin from scalp of AA patients; PS-psoriasis lesional skin; AD- AD lesional skin. N=6 patients for both NL and L, and 4 for PTX.

STUDY DESIGN:

This is a randomized, double-blind, placebo-controlled pilot study of a total of 30 subjects with moderate to severe alopecia areata involving 30-100% of the scalp. We expect 50% of these subjects to have concomitant alopecia areata (AA) and atopic dermatitis (AD).

Subjects with AA alone (15 subjects) will be randomized (2:1) to either receive tralokinumab 300 mg (150 mg/ml) or placebo via subcutaneous injection using 2 pre-filled syringes Q2W for 24 weeks. Subjects with concomitant alopecia areata and atopic dermatitis (15 subjects) will be randomized separately in a 2:1 ratio to receive tralokinumab 300 mg (150 mg/ml) or placebo via subcutaneous injection using 2 pre-filled syringes Q2W for 24 weeks.

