The Principal Investigator will provide safety data to an independent Data and Safety Monitoring Board every 12 months. This DSMB will be comprised of board certified dermatologists who are not directly related to this study. The DSMB will review the data and provide a report of their findings to the Principal Investigator.

EARLY TERMINATION

Any individual whose health or well being may be threatened by continuation in this study will be discontinued by the investigator.

If a female subject becomes pregnant at anytime during the study, she will be discontinued immediately. She will be asked to provide the investigator with medical updates throughout her pregnancy and on the final outcome of the pregnancy.

Any subject who chooses to discontinue the study, or is discontinued from the study by the investigator will be asked to return for a final Early Termination visit for the procedures listed in the Schedule of Events table.

Considering there is no current treatment that is very effective in treating alopecia areata, these subjects are highly motivated to participate in any study that may provide a treatment option. Thus, we have accounted for a 10% drop out rate, and plan to enroll 30 subjects in order to have 27 subjects complete the study.

INVESTIGATIONAL DRUG SUPPLY

In this double-blind study, the investigator will supply tralokinumab (formulated at 150 mg/ml in an isotonic sodium acetate buffer at pH 5.5 in accessorized prefilled syringes for subcutaneous injection) 300 mg for up to 20 subjects and placebo for up to 10 subjects. The tralokinumab and placebo will be provided by MedImmune as 150 mg tralokinumab (and matching placebo) prefilled syringes. Both the 150 mg tralokinumab and the matching placebo prefilled syringes will be of the same quality and identical in size and shape. All study medication will be stored in a secure cool area between 2-8°C. Study drug will be administered to subjects at each visit, and any unused study drug will be kept at the study site. The number of missed doses will be documented for each subject. The investigative site will account for all study drug dispensed and stored during the study.

EFFICACY EVALUATIONS

The following efficacy parameters will be obtained at the previously specified visits:

1. Investigator evaluation of alopecia on the scalp (efficacy of the drug) using the following tools:

Severity Alopecia Tool (SALT)⁵ score:

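### The best set of biomarkers is selected by multiple regression in at most 30 patients with no stated correction for the selection, so any fit reported for that set will be over-optimistic

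*Combined protocol and SAP*

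**What the plan says.** The section Mechanistic Studies Data Analyses describes two steps for skin biopsies. First, "biomarkers will be divided into those that show significant group differences and those that do not"; the groups are not defined there. Second, "Multiple regression models will be used to determine the best set of biomarkers that predict disease activity and response". It then adds: "Similar approaches will be carried out for blood analyses".

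The same section states one correction for multiplicity: "p-values for the moderated t-tests and paired-t-test will be adjusted by Benjamini-Hochberg procedure". It gives no selection algorithm, stopping rule or maximum model size for the regression. Neither it nor any other section mentions cross-validation, bootstrap, permutation, a hold-out sample or external patients for this purpose.

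Study Design describes a "pilot study of a total of 30 subjects with moderate to severe alopecia areata". Early Termination sets out the "plan to enroll 30 subjects in order to have 27 subjects complete the study". Data Analyses calls the study exploratory.

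**The concern.** A model chosen because it fits best looks better in the data that chose it than it will in new patients. The gap grows with the number of candidates and shrinks with the number of patients. Here there are few patients and potentially many candidates: skin is assayed by RT-PCR and gene arrays, and for blood the plan names nine serum cytokines plus RNA and proteomics.

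Benjamini-Hochberg does not close this gap. It limits false discoveries among marker-by-marker tests. It does nothing to the R2, AUC or overall p-value of a multivariable model assembled afterwards.

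At stake is whether a set found in noise is reported as predicting disease activity or response and carried into later work.

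**Working it through.** **Patient numbers.** 30 enrolled with 10% dropout gives 30 × 0.9 = 27 completers, which reproduces the plan's figure. Randomisation 2:1 in two groups of 15 gives 20 on tralokinumab and 10 on placebo. If response is modelled only in treated completers, and dropout is equal across arms (an assumption), n = 20 × 0.9 = 18. The plausible range is therefore n = 18 to 30.

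**Assumptions not in the plan.** Forward selection of k = 3 markers; a continuous outcome; one value per patient; independent normal markers, none related to the outcome. The number of candidates is varied.

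**Formulas.**
- Apparent R2 = 1 − RSS/TSS in the patients used for selection.
- New-patient R2 = the same quantity for the fitted model in 500 simulated new patients.
- Naive test: F = (R2/k) / ((1 − R2)/(n − k − 1)), on k and n − k − 1 degrees of freedom, as if the markers had been fixed in advance.
- For k markers fixed in advance and no association, expected apparent R2 = k/(n − 1); for n = 27 this is 3/26 = 0.12.

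**Results in pure noise.** Each cell gives apparent R2 / new-patient R2 / share of models with naive p<0.05 (1000 datasets per setting, 200 for 1000 candidates).

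| Candidates | n = 30 | n = 27 | n = 18 |
|---|---|---|---|
| 3 (no selection) | 0.10 / −0.16 / 6% | 0.12 / −0.18 / 4% | 0.18 / −0.32 / 5% |
| 6 | 0.18 / −0.27 / 21% | 0.20 / −0.30 / 19% | 0.30 / −0.53 / 19% |
| 10 | 0.25 / −0.36 / 44% | 0.28 / −0.42 / 46% | 0.42 / −0.72 / 52% |
| 20 | 0.34 / −0.50 / 81% | 0.38 / −0.56 / 84% | 0.55 / −0.89 / 87% |
| 50 | 0.46 / −0.67 / 99% | 0.50 / −0.73 / 100% | 0.68 / −1.10 / 100% |
| 1000 | 0.72 / −0.94 / 100% | 0.76 / −1.06 / 100% | 0.91 / −1.22 / 100% |

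The first row confirms that the naive test holds its 5% level when nothing is selected. To see how selection breaks it, take n = 27 and 10 candidates. The average noise model has F = (0.28/3) / (0.72/23) = 2.98, almost at the 5% critical value of 3.03 on 3 and 23 degrees of freedom.

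Larger runs (4000 datasets per setting, 1500 for 50 candidates; markers independent or correlated 0.5) give 20-23% with 6 candidates, 64-71% with 15 and over 99% with 50. Moderate correlation between markers therefore does not change the picture.

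**Binary outcome.** If response is coded as a yes/no outcome such as SALT50 (9/18, 9/27 or 10/30 responders assumed), the best 3 of 6 to 15 noise markers show an apparent AUC of 0.75-0.92.

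**With a real marker.** One marker explaining 20% of the variance among 20 candidates, n = 27: apparent R2 is 0.46 and new-patient R2 is −0.25.

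**Which correction works.** All of these repeat the whole selection each time, in pure noise.
- Leave-one-out cross-validation gives mean R2 of −0.33 to −0.62 (6 candidates) and −0.52 to −1.05 (15), so it does not credit noise with predictive value. The statistic is itself noisy.
- Permutation gives p≤0.05 in 3.8-6.2% of datasets, close to nominal. It tests only whether there is any association and leaves R2 or AUC uncorrected.
- Bootstrap optimism correction is adequate with 6 candidates (n = 18: −0.43 against a new-patient −0.47). It falls short with 15 (−0.43 against −0.89). With 1000 it is about −0.08 against −1.34, where leave-one-out gives −1.43.

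**The case against.** The strongest reply is that this is one sentence of outline in a pilot openly described as exploratory. The plan does not promise an R2, an AUC or a p-value for the chosen set, does not call the set validated, and rests no decision on it. That stands, and it sets the priority. It does not remove the bias: an exploratory label leaves a reported R2 as inflated as before.

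Second, the link between markers and response does not depend on this regression alone. The same section separately correlates expression changes in named pathways (Th2/IL-13, IL-22, S100A7 and S100A8, Th1, Th17) with clinical response through muStat. That analysis does not use the selected set. This also stands.

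Third, the size is not anchored in the plan, because candidate number, model size and rule are all assumed, and repeated measurements per patient were not simulated. The figures show direction and plausible range, and should not be read as a forecast.

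A reader might infer that the group-difference screen is circular as well. The documents do not support that. The groups are undefined, and the section opens with lesional against non-lesional skin, a contrast that uses neither arm nor response. The screen belongs to the selection only if it turns out to use outcome or treatment arm.

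**Conclusion.** The point holds at low severity. The plan commits to selecting a predictive set in at most 30 patients, and the only correction it states does not reach the fit of that set. Any apparent fit or naive p-value reported for it will be over-optimistic. Under the assumptions above, noise alone gives a significant-looking model in about 20% of cases with 6 candidates, 65-70% with 15 and nearly all with 50, with R2 in new patients below zero throughout.

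A reader might go further and conclude that the trial's main results are compromised. They are not: the primary endpoint is change in skin markers, the secondary endpoints are SALT scores and patient questionnaires, and prediction is not a listed endpoint. Nor do the documents show that a spurious predictor will be claimed; that depends on what is reported.

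**What to change.** Add to Mechanistic Studies Data Analyses:

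- The selection rule and the maximum model size are fixed before outcome data are analysed.
- The whole selection procedure, including any screen that uses outcome or treatment arm, is repeated inside every fold of a cross-validation. Folds are formed by patient if repeated measurements are used.
- The cross-validated fit is reported beside or instead of any apparent fit, for skin and for blood.
- Naive p-values of the selected model are not used as evidence of prediction, and the set is described as hypothesis-generating.

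A whole-procedure permutation p-value may be added as a test of no association, but it does not replace the cross-validated fit. Bootstrap optimism correction alone should not be relied on where candidates far outnumber patients, as with gene arrays and proteomics. The candidates may still come from the plan's own screen, whose groups should be named.

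The cost is some analysis code, with no extra patients or samples. Reported performance will be lower, imprecise at this sample size and possibly null. A real predictor can also be missed: with one true marker correlated 0.6 with the outcome (assumed) and 6 to 15 candidates, the whole-procedure permutation test has power of 35-44% at n = 18 and 52-73% at n = 27.
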